7.6.2 Secondary Endpoints

7.6.2.1 Absolute Change in LFC

The absolute change in LFC (assessed by MRI-PDFF) from baseline to Week 36 (V8-EoT) will be analyzed in ANCOVA model adjusting for treatment, T2DM status (T2DM patients versus non-T2DM patients), and NASH CRN fibrosis scoring system (F1 versus F2/F3) and for baseline LFC as a continuous covariate. The method applied to missing data for the primary endpoint in Section 7.6.1.1 will also be utilized for this secondary endpoint. LSMS for treatment groups, standard error of the LSM, pairwise differences (PXL065 7.5 mg QD, 15 mg QD and 22.5 mg QD versus placebo) in LSMS, p-values and 95% CIs will

Statistical Analysis Plan

Sponsor Name: Poxel
Sponsor Protocol ID: PXL065-003

be presented. In addition, descriptive statistics for LFC and change from baseline will be calculated by visit within each treatment group.

The ANCOVA model validity will be checked using appropriate plots (studentized residuals vs predicted values, etc.).

The analysis described in Section 7.6.1.2 and 7.6.1.3, except for the ITTS-w-065-S will also be done for this secondary endpoint.

7.6.2.2 Analysis of Responders

The 4 types of responders that will be analyzed are:

- Absolute reduction in LFC $\geq 5\%$ from baseline to Week 36 (V8-EoT)
- Relative reduction in LFC $\geq 30\%$ from baseline to Week 36 (V8-EoT)
- Relative reduction in LFC $\geq 50\%$ from baseline to Week 36 (V8-EoT)
- LFC value at Week 36 (V8-EoT) that is normalized, i.e. $\leq 5\%$

For each response, responder rate will be provided within each treatment group. The stratified Cochran-Mantel-Haenszel (CMH) will primarily be used to analyze the responders, stratifying for T2DM status (T2DM patients versus non-T2DM patients) and NASH CRN fibrosis scoring system (F1 versus F2/F3). Each PXL065 treatment group will be compared with placebo. The odds ratios (ORs), 95% CIs for the ORs, and p-values will be displayed for the ITTS. In addition, the number of responder's and non-responders will be displayed for each treatment group, see

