2.3 Sample Size and Power

The sample size determination is based on the primary endpoint, i.e. the relative change in LFC (assessed by magnetic resonance imaging – proton density fat fraction [MRI-PDFF] from baseline to Week 36 (V8-End of Treatment [EoT]) ($[\text{LFC}_{\text{W36}} - \text{LFC}_{\text{baseline}}] / \text{LFC}_{\text{baseline}}$) and the primary objective, i.e. to demonstrate the superiority of at least one PXL065 dose to placebo as tested by the following null hypothesis (H_0) versus the alternative hypothesis (H_a):

$$H_0: \mu_{\text{PXL065}} - \mu_{\text{placebo}} = 0 \text{ versus } H_a: \mu_{\text{PXL065}} - \mu_{\text{placebo}} < 0$$

Where μ_{placebo} and μ_{PXL065} denote the mean relative change in the percentage of LFC from baseline to Week 36 in the PXL065 and placebo groups respectively.

The following assumptions will be considered for the sample size determination:

- No adjustment for multiple comparisons between PXL065 doses and placebo will be considered and the usual nominal 1-sided alpha level of 0.025 (or equivalently the 2-sided level of 0.05) will be considered for each PXL065 dose vs placebo comparison
- A power of 90%
- An expected difference $\mu_{\text{PXL065}} - \mu_{\text{placebo}}$ of -30% for at least one PXL065 dose vs placebo comparison
- A standard deviation (SD) of the primary endpoint equal to 30%, as estimated from previous published data
- With these assumptions, a sample size of 23 patients per arm is needed to achieve 90% power for at least one PXL065 dose vs placebo comparison.

Assuming a dropout rate of 20%, around 30 patients per arm ($120 = 4 \times 30$ patients in total) are needed to be randomized.

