7.6 Efficacy

7.6.1 Primary Endpoint

7.6.1.1 Primary Analysis

The primary evaluation of efficacy will be based on MRI-PDFF. The primary endpoint will be the relative change in the percentage of LFC from baseline to Week 36 (V8-EoT) in the ITTS.

For patients who withdraw from the study at or after Week 12 (V4), the LFC will be assessed at ET as far as possible. With the assumption that the LFC assessed at or after Week 12 (V4) reflects what could have been observed at Week 36 (V8-EoT), the missing LFCs at Week 36 (V8-EoT) will be estimated by this value. For patients who withdraw before Week 12 (V4) or withdraw without any LFC assessment at or after Week 12 (V4), LFC missing values at Week 36 (V8-EoT) will be imputed using a multivariate imputation approach by fully conditional specification (FCS) regression method assuming missing at random (MAR) mechanism. The set of variables included in the multiple imputation model will be randomized treatment, type 2 diabetes mellitus status (T2DM patients versus non-T2DM patients), NASH CRN fibrosis scoring system (F1 versus F2/F3), and baseline LFC. The number of imputed datasets generated will be 1000 with the burn-out iterations set at 100. A minimum value of 0 and a maximum value of 50 will also be applied to restrict imputed LFC values, see

Statistical Analysis Plan

Sponsor Name: Poxel
Sponsor Protocol ID: PXL065-003

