Appendix B: Sample SAS® code for analyses of efficacy endpoints for example SAS code.

Each of the complete datasets after imputation will then be analyzed in an analysis of covariance (ANCOVA) model adjusting for treatment and for randomization stratification factors, i.e. T2DM status (T2DM patients versus non-T2DM patients) and NASH CRN fibrosis scoring system (F1 versus F2/F3), and for the baseline LFC as a continuous covariate in the ITTS. Results from each complete dataset will be combined using Rubin's rule to provide the least square means (LSMs) for treatment groups at Week 36, standard error of the LSM, pairwise differences (PXL065 7.5 mg QD, 15 mg QD and 22.5 mg QD versus placebo) in LSMs, p-values and 95% CIs, see

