Appendix B: Sample SAS[®] code for analyses of efficacy endpoints for example SAS code.

Statistical Analysis Plan

Sponsor Name: Poxel
Sponsor Protocol ID: PXL065-003

The binary response will also be analyzed using a logistic regression model adjusting for treatment, stratification factors, i.e. T2DM status (T2DM patients versus non-T2DM patients) and NASH CRN fibrosis scoring system (F1 versus F2/F3), and for the baseline LFC as a continuous covariate. Pairwise differences for each PXL065 treatment group vs placebo will be estimated in the model as ORs along with their p-values and 95% CI. The binary response will also be analyzed using the approach proposed by Ge et al. (2011), see Appendix C: Ge et al. code.

For each type of responder and analysis described above (CMH and logistic regression), two different methods of data handling will be applied:

- Multiple imputation as per Section 7.6.1.1
- No imputation and analysis set restriction (Restricting analysis to only include patients with Week 36 assessments)

Analysis of responder defined as relative reduction in LFC $\geq 30\%$ from baseline to Week 36 (V8-EoT), will be repeated in the ITTS-w-065-S , using multiple imputation as per Section 7.6.1.1.

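### For LFC ≤5% (and, at lower risk, a ≥50% reduction) the planned odds ratios fail if no placebo patient responds, and the readable SAP has no rule for that case

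*SAP*

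**What the plan says.** SAP 7.6.2.2 lists four responses at Week 36: an absolute LFC reduction of at least 5%, relative reductions of at least 30% and at least 50%, and LFC of 5% or less. All four get the same analysis.

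- **Main method.** "The stratified Cochran-Mantel-Haenszel (CMH) will primarily be used to analyze the responders", stratified by T2DM status and fibrosis score, each dose against placebo. "The odds ratios (ORs), 95% CIs for the ORs, and p-values will be displayed for the ITTS".
- **Logistic regression.** Adjusted for treatment, both stratification factors and baseline LFC. Dose-versus-placebo differences "will be estimated in the model as ORs along with their p-values and 95% CI".
- **Third method.** A covariate-adjusted difference in proportions, given by citation, with code in Appendix C.
- **Missing data.** "For each type of responder and analysis described above (CMH and logistic regression), two different methods of data handling will be applied": multiple imputation as in 7.6.1.1, and no imputation ("Restricting analysis to only include patients with Week 36 assessments").

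SAP 7.6.1.1 sets the imputation: "The number of imputed datasets generated will be 1000", with imputed LFC limited to 0 to 50. "Results from each complete dataset will be combined using" Rubin's rule.

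On size, SAP 2.3 says: "Assuming a dropout rate of 20%, around 30 patients per arm". The protocol synopsis plans on at least 24 evaluable patients per arm. Protocol 5.1 requires a screening LFC of at least 8%.

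The readable text names no penalised or exact fit, no continuity correction and no rule for an odds ratio that cannot be computed. The example code in Appendices B and C is blacked out.

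**The concern.** The four definitions differ greatly in how often a placebo patient would meet them. From the lowest permitted baseline of 8%, reaching 5% needs a relative fall of (8 − 5)/8 = 37.5%; from 20% it needs 75%. With 24 to 30 placebo patients, an arm with no responder is plausible.

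The Mantel-Haenszel odds ratio then has no finite value, and the maximum-likelihood logistic estimate diverges. Software stops at its iteration limit and may still print a number. Imputation does not repair this. A minority of imputed datasets contain a placebo responder and give finite estimates; the rest contribute arbitrary numbers with huge standard errors, and Rubin's rule averages the two kinds.

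At stake are the odds ratio and its interval for a listed secondary endpoint. One display could show a small CMH p-value beside a logistic p-value near 1, and the remedy would then be chosen after unblinding.

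**Working it through.** **1. The plan's sample size.** With a difference of 30, SD 30 and two-sided alpha 0.05, the two-sample t-test has power 0.8997 at 22 per arm and 0.9125 at 23. The stated 23 is right. Allowing for 20% dropout, 23/0.8 = 28.75 and 24/0.8 = 30, which agrees with about 30. The plan gives no expected rate for any responder endpoint.

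**2. Chance of no placebo responder.**
- From the documents: SD of relative change 30%; baseline LFC ≥8%; 24 evaluable or 30 randomized placebo patients.
- Assumed, because the documents give neither: baseline b = 8 + a gamma variable (shape 2) with overall mean 12.5, 15, 17.5 or 20%; placebo mean change μ = 0, −10 or −15%.

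Formulas:
- p(LFC ≤5%) = average over b of Φ((100(5/b − 1) − μ)/30)
- p(≥50%) = Φ((−50 − μ)/30), and likewise with 30 for the ≥30% definition
- P(no responder) = (1 − p)^n

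| Definition | Assumptions | p | n = 24 | n = 30 |
|---|---|---|---|---|
| LFC ≤5% | mean baseline 20, μ = 0 | 0.0135 | 72% | 66% |
| LFC ≤5% | mean baseline 12.5, μ = −15 | 0.0863 | 11% | 7% |
| ≥50% | μ = 0 | 0.048 | 31% | 23% |
| ≥50% | μ = −10 | 0.091 | 10% | 6% |
| ≥50% | μ = −15 | 0.122 | 4% | 2% |
| ≥30% | μ = 0 (worst case) | 0.159 | 1.6% | 0.6% |

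A separate calculation used a truncated normal baseline (mean 15 to 22, SD 5 to 7) and μ = 0 to −10, with the same SD of 30%. It gave 38% to 81% for LFC ≤5% at n = 24, and 0.01% to 2.8% for the absolute ≥5% definition.

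**3. Mantel-Haenszel.** OR = Σ(a·d/N) / Σ(b·c/N) over strata, where a and b are responders and non-responders on the dose, and c and d the same on placebo. If c = 0 in every stratum, the denominator is exactly 0.

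**4. Logistic regression without imputation.** For 0/24 against 4/24 with no covariates, the log odds ratio is 7.6 (SE 20) after 8 iterations, 14.6 (SE 673) after 15 and 24.6 (SE about 100,000) after 25. The estimate measures the iteration limit, not the data.

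**5. One simulated trial with 1000 imputations.** LFC ≤5%, 6 of 30 missing per arm, 0 observed placebo responders and 4 at the top dose. CMH on observed patients: chi-square 3.74, p = 0.053. The Mantel-Haenszel denominator was zero in 859 of 1000 imputed datasets. Pooled results:

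| Method | log OR | SE | p |
|---|---|---|---|
| Ordinary, 8 iterations | 6.54 | 15.0 | 0.66 |
| Ordinary, 15 iterations | 12.55 | 493 | 0.98 |
| Ordinary, 25 iterations | 21.14 | 73,186 | 1.00 |
| Firth | 2.27 | 1.51 | 0.13 |

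Pooling only the 141 datasets with a placebo responder gives log OR 1.66 (OR 5.2). That selects the datasets in which placebo patients happened to be imputed as responders.

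**6. Wider simulation.** Four arms of 30; doses assumed 10, 20 and 30 points better than placebo; 50% T2DM and 35% F1; 10% or 20% of Week 36 values missing at random (20% is the plan's dropout; early-termination scans would lower it); imputation on the SAP's variables with limits 0 to 50, using 100 imputations. For LFC ≤5%, 24 scenarios × 150 = 3,600 trials had no observed placebo responder and at least one at the top dose. Ranges of scenario medians, top dose against placebo:

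- Mantel-Haenszel OR estimable in 8% to 19% of imputed datasets at 10% missing and 16% to 38% at 20% missing; in no trial was it estimable in all of them.
- Ordinary logistic, 8 iterations: log OR 6.0 to 7.5, SE 14 to 17, p 0.64 to 0.69 (smallest in any trial 0.34).
- Ordinary logistic, 25 iterations: log OR 17 to 22, SE 68,000 to 81,000, p about 1.
- Firth: log OR 1.9 to 3.2, SE 1.45 to 1.52, p 0.03 to 0.22.
- CMH on observed patients (10% missing): p 0.002 to 0.11.

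For ≥50% (6 × 150 = 900 trials), ordinary logistic at 8 iterations gave log OR 6.1 to 7.6 with p 0.63 to 0.68; Firth gave 2.6 to 3.5 with SE 1.42 to 1.45.

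**7. Adjusted difference in proportions, 5/30 against 0/30.** The ordinary fit gives a difference of 0.167 (SE 0.068), but the placebo risk has SE 0.002 at 8 iterations and below 0.000001 at 25. The Firth fit gives placebo risk 0.021 (SE 0.026) and a difference of 0.181 (SE 0.078).

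**The case against.** **The rule may be in the redacted code.** The section points to Appendices B and C, both blacked out, and a penalised or exact option would naturally sit there. This stands, and is why the request can be met with one confirming sentence. The variance method for the adjusted difference cannot be judged from the readable text either, so that part is only a clarification.

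**The probabilities rest on assumptions.** True: only the SD of 30% and the 8% entry limit are sourced. But two different sets of baseline assumptions both give a material risk for LFC ≤5%, and the algebraic failure needs no assumption once the placebo count is zero.

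**Little is lost.** The CMH test, the responder counts and the adjusted difference remain, the failure would be visible, and the protocol describes a Phase 2 trial for internal decision. This stands and limits the point to minor.

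**Firth everywhere is more than is needed.** On the figures above, a placebo responder is present in 28% to 93% of trials for LFC ≤5% and 69% to 98% for ≥50%, and there Firth shrinks a finite estimate. Alternatives such as exact logistic regression exist. The cost is real, but naming one estimator in advance avoids a switch driven by the data.

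**The CMH p-value under imputation.** The p-values above are for observed patients, and 7.6.2.2 does not say how CMH results are combined over imputations. That is a fair, separate gap. In the six trials run with 1000 imputations the CMH chi-square was computable in every imputed dataset.

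**Conclusion.** The concern holds, as a conditional and minor point. If no placebo patient reaches LFC ≤5%, the readable plan gives no usable odds ratio or confidence interval for that secondary endpoint: Mantel-Haenszel is not estimable in most imputed datasets, and the pooled ordinary logistic result has no meaning. The chance of this is 11% to 72% with 24 placebo patients and 7% to 66% with 30, assuming mean baseline LFC of 12.5 to 20%, placebo change of 0 to −15% and the plan's SD of 30%. For ≥50% it is 4% to 31% and 2% to 23%. The ≥30% definition is essentially unaffected. Excluding one site from the ITTS reduces the placebo arm by a number the documents do not give, which can only raise the risk. Confidence is medium, because the placebo rate is assumed and the code is not visible.

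**What to change.** Change SAP 7.6.2.2 only:

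1. For LFC ≤5% and ≥50% reduction, fit the logistic models with Firth's penalised likelihood, in every imputed dataset and in the analysis restricted to patients with Week 36 data.
2. Report the Mantel-Haenszel odds ratio as not estimable when it cannot be computed in some imputed datasets. Do not pool over the estimable ones alone.
3. As a clarification, confirm that the adjusted difference in proportions uses the same two data-handling methods, and that its interval carries placebo-arm uncertainty when that arm has no responder. Deriving it from the same Firth fit does this.

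CMH stays the primary test. If the blacked-out code already covers this, one sentence saying so is enough.

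The cost is two or three sentences and a standard software option, with no new data. There is a statistical price. Where both fits were finite, the Firth log odds ratio was a median 12% to 26% smaller for LFC ≤5% and 10% to 18% smaller for ≥50%. Its pooled Wald p-value is conservative (1 rejection in 6 × 600 = 3,600 null trials), so it should not replace the CMH p-value.

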Appendix B: Sample SAS[®] code for analyses of efficacy endpoints for example SAS code.

Statistical Analysis Plan

Sponsor Name: Poxel
Sponsor Protocol ID: PXL065-003

The binary response will also be analyzed using a logistic regression model adjusting for treatment, stratification factors, i.e. T2DM status (T2DM patients versus non-T2DM patients) and NASH CRN fibrosis scoring system (F1 versus F2/F3), and for the baseline LFC as a continuous covariate. Pairwise differences for each PXL065 treatment group vs placebo will be estimated in the model as ORs along with their p-values and 95% CI. The binary response will also be analyzed using the approach proposed by Ge et al. (2011), see Appendix C: Ge et al. code.

For each type of responder and analysis described above (CMH and logistic regression), two different methods of data handling will be applied:

- Multiple imputation as per Section 7.6.1.1
- No imputation and analysis set restriction (Restricting analysis to only include patients with Week 36 assessments)

Analysis of responder defined as relative reduction in LFC $\geq 30\%$ from baseline to Week 36 (V8-EoT), will be repeated in the ITTS-w-065-S , using multiple imputation as per Section 7.6.1.1.

7.6.2.3 Other Secondary Continuous Endpoints

Efficacy will be further assessed based on the following secondary continuous endpoints:

- Liver enzymes: ALT, AST, GGT, ALP
- Measured glycemic parameters: FPG, HbA1c, serum insulin, C-peptide
- Insulin resistance indexes: HOMA-IR, QUICKI, HOMA- β , Adipo-IR

The change from baseline (Randomization Visit [V1]) to Week 36 (V8) will be analyzed using a Mixed Model for Repeated Measures (MMRM) for the secondary continuous parameters with fixed effects for treatment, stratification factors, i.e. T2DM status (T2DM patients versus non-T2DM patients) and NASH CRN fibrosis scoring system (F1 versus F2/F3), baseline endpoint specific parameter value, time-point, and treatment by time-point interaction. Covariance parameters will be estimated via the REML method. Compound symmetry will be used for the covariance structure. The Kenward and Roger's method for evaluating the degrees of freedom will also be used. Example SAS code is shown in Appendix C.

All patients in the ITTS with non-missing baseline data and at least one post-baseline data are included in the analysis mode, which uses values at all time points with data available. The MMRM analyses will use observed data only, no imputations of data will be performed.

The LSMS for change from baseline at Week 36 and LSM differences for change from baseline between PXL065 treatment groups and placebo will be presented along with 95% CIs and the comparison p-value. A two-sided nominal significance level of 0.05 will be used for treatment comparison.

In addition, the results and changes from baseline at scheduled visits will be summarized by treatment group and visit using standard descriptive statistics for the ITTS.

The same statistical analyses described above will be repeated for the ITTS-w-065-S for the following secondary continuous endpoints:

- Liver enzymes: ALT, AST

CONFIDENTIAL

Statistical Analysis Plan

Sponsor Name: Poxel
Sponsor Protocol ID: PXL065-003

- Measured glycemic parameters: FPG, HbA1c

A listing of secondary continuous efficacy endpoint data will be produced for the ITT set with site 065-S .

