## 4 Study Design

### 4.1 Study Design and Schedule

This study is a Phase 2, multi-center, double-blind, placebo-controlled, randomized study with 4 parallel groups in noncirrhotic, biopsy-proven NASH patients.

There will be a total of 3 study periods, as follows:

- Screening Period: maximum of 8 weeks

The screening period can be exceptionally extended after approval of the medical monitor and the POXEL medical representative, if there is no more than 10 weeks between MRI-PDFF and Randomization Visit (V1).

- Double-blind treatment period: 36 weeks
- Follow-up period: 2 weeks

Patients will be randomized in a 1:1:1:1 ratio to receive either:

- PXL065 7.5 mg oral QD
- PXL065 15 mg oral QD
- PXL065 22.5 mg oral QD
- Placebo oral QD

Randomization will be stratified according to T2DM status (T2DM patients versus non-T2DM patients) and the NASH Clinical Research Network (CRN) fibrosis scoring system (F1 versus F2/F3). This study will have to include at least 50% of T2DM patients and a maximum 35% of F1 patients.

The diagram of the study design is shown in *Figure 1* and the visit schedule is tabulated in *Table 1*.

The duration of study for each patient from the first visit for the informed consent signature (ICF) up to the end of the Follow-up period will be between 40 and 46 weeks.

The end of study (EoS) is defined as the date of last visit of last patient participating in the study.

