#### 6.2.2 Follow-up Period

The Follow-up period starts at the end of the 36-week double-blind treatment period. At the End-of-Treatment Visit (V8-EoT), patients will not receive an IMP kit and consequently they will not take IMP during the follow-up period.

The Follow-up period will last for 2 weeks.

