7.6.2.5 Subgroup Analysis

Analysis of responder defined as relative reduction in LFC $\geq 30\%$ from baseline to Week 36 (V8-EoT), will have a subgroup analysis performed using multiple imputation as per Section 7.6.1.1 for the following groups:

- Randomization strata of T2DM status (T2DM patients, non-T2DM patients)
- Randomization strata of NASH CRN fibrosis scoring system (F1, F2/F3)

The MMRM analysis described in Section 7.6.2.3 will have subgroup analysis performed for the following parameters and subgroups in the ITT Set:

- ALT (U/L)
 - Randomization strata of T2DM status (T2DM patients, non-T2DM patients)
 - Randomization strata of NASH CRN fibrosis scoring system (F1, F2/F3)
- AST (U/L)
 - Randomization strata of T2DM status (T2DM patients, non-T2DM patients)
 - Randomization strata of NASH CRN fibrosis scoring system (F1, F2/F3)
- FPG (mmol/L)
 - Randomization strata of T2DM status (T2DM patients, non-T2DM patients)
- HbA1c (%)
 - Randomization strata of T2DM status (T2DM patients, non-T2DM patients)

Statistical Analysis Plan

Sponsor Name: Poxel
Sponsor Protocol ID: PXL065-003

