7.6.3 Exploratory Endpoints

The analyses described in Section 7.6.2.3 will be repeated for the ITTS for the following endpoints:

- Adiponectin
- Lipids (Percentage change): total cholesterol, LDL-c, HDL-c, triglycerides, FFA
- Biomarker of inflammation: hsCRP

For lipids (total cholesterol, LDL-C, HDL-C, triglycerides and FFA) summary statistics will be provided for both, absolute and percent change from baseline.

Biomarkers of fibrosis (pro-C3, NFS, FIB-4 and ELF score) will be analyzed using a linear regression with the following covariates, treatment, T2DM status (T2DM patients versus non-T2DM patients) and NASH CRN fibrosis scoring system (F1 versus F2/F3), and for the baseline endpoint specific parameter value. LSMs for treatment groups, standard error of the LSM, pairwise differences (PXL065 7.5 mg QD, 15 mg QD and 22.5 mg QD versus placebo) in LSMs, p-values and 95% CIs will be presented. In addition, descriptive statistics for each parameter and change from baseline will be calculated by visit within each treatment group.

The change from baseline in NAS, in each component of NAS (steatosis, ballooning and inflammation), total NAS score and in NASH CRN fibrosis score will be analyzed using a non-parametric ANCOVA method of Koch, Tangen, Jung, and Amara (Koch et al), with fixed effects for treatment, stratification factors, i.e. T2DM status (T2DM patients versus non-T2DM patients) and NASH CRN fibrosis scoring system (F1 versus F2/F3), baseline endpoint specific parameter value. This analysis will be performed using the SAS macro for non-parametric randomization-based ANCOVA 'NParCov4'. An example of the SAS code is given below:

Corporate confidential information

Note: The variance under the null (HYPOTH=NULL) will be the structure for producing p-values, while the variance under the alternative (HYPOTH=ALT) will be used for computing confidence intervals.

Total NAS score is the sum of three scores:

- Steatosis (0-3)

CONFIDENTIAL

Statistical Analysis Plan

Sponsor Name: Poxel
Sponsor Protocol ID: PXL065-003

- Ballooning (0-2)
- Inflammation (0-3)

The statistical model will be used to calculate the treatment difference (PXL065 - placebo), 95% CI and p-value at Week 36

The number of percentage of patients in each category below from baseline to Week 36 will also be presented by treatment group on the ITTS:

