7.7.5 Vital Signs and Body Measurements

The following vital sign and body measurements will be taken during the study:

- height (cm)
- weight (kg)
- waist circumference (cm)
- hip circumference (cm)
- Waist-to-hip ratio [Derived as waist circumference (cm)/hip circumference (cm)]
- heart rate (bpm)
- SBP (mmHg) with 3 readings
- DBP (mmHg) with 3 readings

The following vital sign results are derived on the eCRF:

- calculated BMI (kg/m^2)
- mean SBP (mmHg)
- mean DBP (mmHg)

Vital signs data and changes from baseline in vital signs will be summarized visit by using standard descriptive statistics for each treatment group the Safety set. For summaries, the average of the 3 blood pressure readings will be used.

Summary table on weight will be repeated in the Safety set with site 065-S: .

Statistical Analysis Plan

Sponsor Name: Poxel
Sponsor Protocol ID: PXL065-003

The MMRM analysis described in Section 7.6.2.3 will be repeated for the Safety set, Safety set with site 065-S and ITTS for weight (kg).

A listing of vital signs data will be produced for the Safety set with site 065-S .

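### The SAP fixes compound symmetry for every MMRM, with no stated fallback or robust variance, so Week 36 confidence intervals and p-values can be miscalibrated in either direction

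*SAP*

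**What the plan says.** SAP 7.6.2.3 analyses change from baseline in liver enzymes, glycemic parameters and insulin-resistance indexes with an MMRM. The fixed effects are treatment, the two stratification factors, baseline value, visit and treatment by visit. Three statements matter here:

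- Estimation: "Covariance parameters will be estimated via the REML method", with Kenward-Roger degrees of freedom.
- Covariance: "Compound symmetry will be used for the covariance structure". No condition is attached.
- Data: the model is one "which uses values at all time points with data available", although the analysis is described as change to Week 36. The reported result is the Week 36 difference from placebo, with a 95% CI and a nominal two-sided 5% p-value.

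Other sections import the model by reference:

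- 7.6.2.5: "The MMRM analysis described in Section 7.6.2.3 will have subgroup analysis performed for the following parameters and subgroups in the ITT Set" (ALT and AST by diabetes and fibrosis strata; FPG and HbA1c by diabetes stratum).
- 7.6.3: "The analyses described in Section 7.6.2.3 will be repeated for the ITTS for the following endpoints" (adiponectin, lipids, hsCRP).
- 7.7.5, for body weight: "The MMRM analysis described in Section 7.6.2.3 will be repeated for the Safety set, Safety set with site 065-S", and also for the ITTS.

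The code in Appendices B and C is blacked out, so the absence of a fallback is a statement about the readable text.

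**The concern.** Compound symmetry assumes the same variance at every visit and the same correlation between every pair of visits. For change from baseline, neither needs to hold over 36 weeks. The variance assumption matters most, because the model uses one pooled variance for the Week 36 contrast. Kenward-Roger adjusts for small samples within the assumed structure; it does not repair a wrong structure.

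Which visits are pooled is also unclear. SAP 6.1 (Tables 1 and 2) gives weight, the safety laboratory panel (which includes the liver enzymes and hsCRP) and FPG a Week 38 window. By then, under Protocol 6.2.2, "patients will not receive an IMP kit and consequently they will not take IMP during the follow-up period". HbA1c, insulin, C-peptide, the indexes, adiponectin and lipids have no Week 38 window, so for them the question does not arise.

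At stake are the Week 36 interval and p-value for every endpoint listed above. Weight is the most exposed, because it is measured at every visit from Week 3. It also matters to the trial's argument: Protocol 4.2 looks to weight to confirm reduced PPARγ activity, and describes the study as informing Phase 3 dose choice.

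**Working it through.** **Inputs from the documents.** SAP 2.3 plans 23 evaluable patients per arm and about 30 randomized. This reproduces: for a difference of 30, SD 30 and two-sided 5%, exact t-test power is 89.97% at n = 22 and 91.2% at n = 23; 23/(1 − 0.20) = 28.75, so about 30. That calculation concerns the primary endpoint only. No SD, correlation or standard error is given for any MMRM endpoint, so **every variance pattern below is an assumption**.

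**Closed form, complete data.** Let σ_t be the SD of change at visit t. Under compound symmetry the Week 36 standard error uses the mean of σ_t² over the modelled visits, so

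- ratio of model SE to true SE: R = √(mean σ_t² / σ²_W36)
- true two-sided error of a nominal 5% test: 2·(1 − Φ(1.96·R))

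Worked example, SD 0.8/0.9/1.0 at Weeks 12, 24 and 36: mean variance = (0.64 + 0.81 + 1.00)/3 = 0.817; R = √0.817 = 0.904; error = 2·(1 − Φ(1.771)) = 7.7%. Reversed, SD 1.0/0.9/0.8: R = √(0.817/0.64) = 1.130; error 2.7%.

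| Assumed SD pattern | To Week 36 | With Week 38 added |
|---|---|---|
| Labs, 1.0/0.9/0.8 (then 0.8) | 2.7% | 3.1% |
| Labs, constant | 5.0% | 5.0% |
| Labs, 0.9/1.09/1.0 (average equals Week 36) | 5.0% | – |
| Labs, 0.9/1/1 | 5.8% | – |
| Labs, 0.9/0.95/1 (then 1) | 6.2% | 5.9% |
| Labs, 0.8/0.9/1 (then 1) | 7.7% | 6.9% |
| Labs, variance proportional to time | 11.0% | 8.7% |
| Weight, falling evenly 1.0 to 0.8 (then 0.8) | 2.7% | 2.9% |
| Weight, 0.8/0.9 then 1 from Week 12 | 6.0% | 5.9% |
| Weight, variance proportional to time | 16.1% | 13.6% |

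Last row: the mean of 3, 6, 12, 18, 24, 30 and 36, divided by 36, is 0.512, so R = 0.715; adding Week 38 gives 0.580 and R = 0.761.

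**Fitted models with dropout.** Settings: no true effect, four arms of 30, treatment by visit, baseline and two strata, REML, Kenward-Roger, monotone dropout reaching 20% by Week 36. There were 3,000 to 3,200 replicates with three dose comparisons each; Monte Carlo error was about 0.2 to 0.4 points.

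| Scenario | Compound symmetry | Unstructured |
|---|---|---|
| Labs, falling | 2.3% | 4.6–4.7% |
| Labs, constant | 4.9% | 4.6–4.7% |
| Labs, mild rise (two patterns) | 5.5–5.9% | 4.6–4.7% |
| Labs, 0.8/0.9/1 | 7.6% | 4.6–4.7% |
| Labs, proportional to time | 11.9% | 4.6–4.7% |
| Weight to Week 36, plateau | 7.2% | 5.1% |
| Weight to Week 36, proportional to time | 18.4% | 4.8% |
| Weight with Week 38, proportional to time | 16.6% | 5.6% |
| F1 subgroup, 10 per arm, 0.8/0.9/1 | 8.0% | 5.3% |

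The F1 size follows from Protocol 4.1 ("This study will have to include at least 50% of T2DM patients and a maximum 35% of F1 patients"): 35% of 120 is 42, or about 10 per arm. These fitted figures also depend on an assumed within-patient correlation, whose value is not recorded with the results. The closed-form figures do not depend on it and are the ones to reproduce.

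**Cross-check with stated correlations.** A separate simulation (1,500 replicates, 20% dropout, approximate degrees of freedom) used correlation 0.7 per six weeks for labs and 0.85 for weight. With equal variances and only the correlation pattern wrong, compound symmetry gave 5.3%. HbA1c with SD 0.7/0.85/1 gave 10.3%, and with 1.3/1.15/1 gave 2.2%. Weight with Week 38, proportional to time, gave 15.5%. An ANCOVA on observed Week 36 data, which estimates that variance directly, gave 4.2% to 5.5% throughout. Unequal variance is therefore the condition that matters.

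**The case against.** The documents do not show that the variances differ. Compound symmetry is a recognised, parsimonious choice in a small trial, and several patterns above give 5% or a conservative test. This stands: the point is conditional, and the direction cannot be known from the documents.

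The largest weight figures assume variance proportional to time, which puts the Week 3 SD at √(3/36) = 29% of the Week 36 SD; for labs, Week 12 is √(12/36) = 58%. Nothing in the documents supports so steep a rise. These are extremes, and the mild-to-moderate rows deserve more weight.

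The consequences are also bounded. The affected analyses are secondary, exploratory or safety, at nominal 5%, in a Phase 2 trial that Protocol 9.1 describes as being for internal decision. With complete data the estimated treatment differences do not depend on the covariance structure. Visit means and SDs will be tabulated, so unequal variance would be visible. That is true, but seeing it does not correct the reported intervals and p-values.

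Finally, an unstructured matrix might be thought too costly at this size. A further REML check with 20% dropout (400 replicates, approximate degrees of freedom) gave compound symmetry 5.0%, 9.0% and 3.6% for constant, rising and falling SDs, against 4.6%, 6.1% and 5.6% unstructured. With constant variance the unstructured SE was 0.4% wider, or 0.9% at 10 per arm. The cost objection does not hold.

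**Conclusion.** The concern holds as a conditional statement and should be fixed. As written, the Week 36 intervals and p-values from every MMRM are right only if the Week 36 variance equals the average over the modelled visits. Under mild-to-moderate assumed departures the closed-form error of a nominal 5% test runs from about 2.7% to 7.7%. Under variance proportional to time it reaches 11.0% for labs and 16.1% for weight.

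The limits are these. All SD patterns are assumed. Thirty per arm is the planned number; the ITTS will be smaller by the excluded site, whose size is not given. Blacked-out code could contain a fallback that the text does not mention. The primary ANCOVA, the responder analyses, the fibrosis-biomarker regression and the histology analyses do not use this model.

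**What to change.** In SAP 7.6.2.3, replace the covariance sentence with wording such as:

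> An unstructured covariance matrix will be used. If it fails to converge, heterogeneous Toeplitz and then heterogeneous AR(1) will be used, in that order. The same rule applies to the subgroup models (7.6.2.5), the exploratory endpoints (7.6.3) and body weight (7.7.5).

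Keep REML and Kenward-Roger. Add a sentence stating whether Week 38 values enter the models for weight, FPG and the safety-panel parameters.

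The cost is a short text change, the covariance option in the code and programming of the fallback sequence; no new data are needed. With constant variance, where compound symmetry would have been right, the unstructured model widened the average Week 36 standard error by 0.6% (labs, 30 per arm) and 1.1% (F1, 10 per arm). No unstructured fit failed in 3,000 weight fits or 3,200 F1 fits per scenario. Real data with irregular missingness, or a smaller ITTS, may still need the fallback; the fallback structures themselves were not simulated.
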